8.2 Per Protocol Analysis Set (PPAS)

The per protocol analysis set will include all patients meeting the FAS criteria in addition to the following criteria:

- Meeting all the inclusion and none of the exclusion criteria
- Having no major protocol deviations

- [REDACTED]
- [REDACTED]

8.3 Safety Analysis Set (SAS)

The safety analysis set will include all patients exposed to OTL38.

8.4 Evaluable Lesions

Evaluable lesions are defined as follows: lesions that do not appear on an organ or tissue that was intended for removal regardless of the absence or presence of tumor based on the Pre-Fluorescence Surgical Plan.

The primary efficacy endpoint will be determined based on evaluable lesions for FAS subjects.

Unless otherwise specified, exploratory efficacy endpoints [REDACTED]

[REDACTED] sensitivities, FPRs, and PPVs for FR+ with ovarian cancer and other disease+/test+ configurations will be estimated using lesions without regard to evaluable lesion status.

Efficacy endpoints calculated without input from lesion data will be estimated without regard to evaluable lesion status.

8.5 Pharmacokinetic Analysis Set

All patients receiving a full dose of OTL038 and with one or more measurable drug-plasma concentrations will be included in the PK Analysis Set.

9 SUBJECT DISPOSITION AND PROTOCOL DEVIATIONS

9.1 Subject Disposition

Patient disposition will be summarized and include the following:

- The number of patients signing informed consent
- The number and percent of patients exposed to study drug
- The number and percent of patients randomized to each group
- The number and percent of patients who completed the study overall and by randomized group assignment

- The number and percent of patients who did not complete the study and the reason for early withdrawal overall and by randomized group assignment

Patients will be considered enrolled if they sign the informed consent (IC) and are exposed to study drug. Patients who signed the IC and receive study drug will serve as the denominator for the calculation of percentages. An exception will be the percentages calculated for early withdrawal reasons which will be based on the number of patients not completing the study. A data listing for all enrolled patients with regard to disposition will also be provided.

Patients who sign the IC but are not exposed to study drug will not be represented in any further analyses or line listings.

9.2 Protocol Deviations

All protocol deviations will be recorded on the protocol deviation case report from (eCRF) and will be reported in line listings. Major protocol deviations will be identified prior to database freeze for the final analysis of endpoints other than [REDACTED] (see Section 15; Interim Analyses and Data Monitoring). Major protocol deviations will be analyzed by aggregate summary and line listings. For aggregate summaries, data will be presented overall and by randomized group assignment and for each analysis population. If the number of major protocol deviations is small, aggregate summaries will not be presented.

10 SUBJECT DEMOGRAPHICS AND BASELINE CHARACTERISTICS

Descriptive statistics for patient demographics and baseline disease status will be provided. Demographics will be grouped by patients exposed to OTL38, patients randomized to no fluorescent light imaging, and patients randomized to undergo fluorescent light imaging, and overall randomized groups. If all patients exposed to OTL38 are subsequently randomized, the separate category for patients exposed to OTL38 may be omitted. Demographic variables will include, but are not limited to: age, sex, and race/ethnicity.

Baseline characteristics will include, but are not limited to: medical history, ovarian cancer history, ovarian cancer type, ovarian cancer stage, height, weight, and body mass index (BMI). Summaries will be tabulated for the mITT (FAS) group and the Safety Analysis Set. Individual demographic and baseline characteristics data will also be presented in line listings.

11 MEASUREMENTS OF TREATMENT COMPLIANCE

Study drug is administered as a single infusion. The number of patients signing the IC but not receiving study drug will be presented in the disposition summary. For patients exposed to study drug, the dose received will be listed in the study drug administration line listing.

[figure not shown]
12 EFFICACY EVALUATIONS

12.1 Primary Efficacy Endpoint

The primary efficacy endpoint is the proportion of patients with at least one evaluable FR+ ovarian cancer lesion confirmed by [REDACTED] pathology [REDACTED] that was detected using the combination of OTL38 and fluorescent light but not under normal light or palpation. [REDACTED]

12.2 Secondary Efficacy Endpoints

- False Positive Rate at the patient level (FPRp) will be a major secondary efficacy endpoint and is defined as the proportion of folate positive ovarian cancer patients in whom all lesions, without regard to evaluable lesion status, detected by fluorescent light only are histologically negative.
- Sensitivity or True Positive Rate (TPR) for OTL38 in combination with fluorescent light: [REDACTED]
- False Positive Rate (FPR) for OTL38 in combination with fluorescent light: For the purpose of this protocol, [REDACTED]

12.3 Exploratory Endpoints

- [Redacted]
- [Redacted]
- [Redacted]
- [Redacted]
- [Redacted]
- [Redacted]
- [Redacted]
- [Redacted]
- [Redacted]

- [REDACTED]
- [REDACTED]
- [REDACTED]
- [REDACTED]
 - [REDACTED]
 - [REDACTED]
- [REDACTED]
- [REDACTED]

12.4 Safety Endpoints

- Incidence rates of treatment-emergent AEs (TEAEs), SAEs, and Adverse Device Effects (ADEs), and changes in clinical laboratory values, vital signs, physical examination, concomitant medications and ECG through Visit 4.

12.5 Pharmacokinetic Endpoints

- Primary plasma pharmacokinetic (PK) parameters for OTL38, including systemic clearance (CL), volume of distribution of the central and peripheral compartments (V_c , V_p), and distributional clearance(s) (CL_d), on a population and individual patient level.
- Effects of patient specific covariates (e.g. baseline demographics and laboratory value indicators of renal and hepatic function) upon PK parameters, reported as coefficients demonstrating significance at the alpha level of 0.05.

13 STATISTICAL ANALYSIS METHODS FOR EFFICACY

The primary analysis of the primary efficacy endpoint will be conducted using the evaluable lesions for FAS subjects. Analyses of secondary and exploratory efficacy endpoints will use the FAS with additional, or modified, criteria as appropriate and as described in Section 8.4 and below. Baseline values are defined as the last non-missing value for a particular efficacy endpoint recorded prior to exposure to study drug. Unless otherwise noted, all p-values will be two-tailed and all confidence intervals two-sided.

13.1 Analytic Methods for the Primary Efficacy Endpoint

The primary analysis of the primary efficacy endpoint will be a one-sample test for a proportion via an exact binomial test conducted at the two-tailed alpha level of 0.05. [REDACTED]

13.1.1 Description of Subgroups to be Analyzed

Using the FAS, descriptive summary statistics for the primary efficacy endpoint will also be provided for the following subgroups:

- Age: < 70 Yrs. Vs. ≥ 70 Yrs.
- Race/Ethnicity
- Study Center
- Imaging System, if applicable
- [REDACTED]
- [REDACTED]
- Stage of Cancer: 1 through 4
- Miliary vs. Non-Miliary Disease

For each subgroup, the point estimate and the exact 95% CI for the primary efficacy endpoint will be provided. These subgroup analyses will be conducted only if the subgroup sample sizes are large enough to provide meaningful summary statistics.

13.1.2 Sensitivity Analyses for the Primary Efficacy Endpoint

Sensitivity analyses for the primary efficacy endpoint will be conducted separately for the Per-Protocol analysis set. The analytic methods will follow those outlined for the primary analysis and include only evaluable lesions.

13.2 Analytic Methods for Secondary Efficacy Endpoints

The patient level False Positive Rate (FPR_p) will be analyzed descriptively, providing the point estimate and the two-sided 95% Wilson (score) confidence interval. The analysis will be conducted using the FAS.

[REDACTED]

[REDACTED]

[REDACTED]

[REDACTED]

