5.2.2 Exclusion

Patients will be excluded if they meet any of the exclusion criteria listed below:

1. Previous exposure to OTL38
2. Known FR-negative ovarian cancer
3. Planned surgical debulking via laparoscopy or robotic surgery, with no intent of laparotomy
4. Patients with known ovarian cancer miliary disease determined pre-operatively to be inoperable
5. Any medical condition that in the opinion of the investigators could potentially jeopardize the safety of the patient
6. History of anaphylactic reactions
7. History of allergy to any of the components of OTL38, including folic acid
8. Pregnancy or positive pregnancy test
9. Clinically significant abnormalities on the electrocardiogram (ECG)
10. Presence of any psychological, familial, sociological or geographical condition potentially hampering compliance with the study protocol and follow-up schedule
11. Impaired renal function defined as $eGFR < 50 \text{ mL/min/1.73m}^2$
12. Impaired liver function defined as values $> 3x$ the upper limit of normal (ULN) for alanine aminotransferase (ALT), aspartate aminotransferase (AST), alkaline phosphatase (ALP), or total bilirubin.
13. Known Stage IV ovarian cancer with brain metastases
14. Received an investigational agent in another clinical trial within 30 days prior to surgery
15. Known sensitivity to fluorescent light

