3 OVERALL STUDY DESIGN

This is a phase 3, randomized, multi-center, single dose, open label, pivotal study in patients diagnosed with, or with high clinical suspicion of, ovarian cancer scheduled to undergo primary surgical cytoreduction, interval debulking, or recurrent ovarian cancer surgery.

All patients participating in the study are expected to receive OTL38 and undergo normal light evaluation; however, to guard against the possible “under-calling” of lesions during the normal light assessment, patients will be randomized to a no fluorescent imaging group. [REDACTED]

Efficacy will be assessed for patients undergoing both normal light and fluorescent light imaging. All patients exposed to OTL38, regardless of randomized group assignment, will be followed for safety. Further details are provided in the protocol.

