4 STUDY POPULATION

The study population will consist of adult female patients diagnosed with, or with a high clinical suspicion of, ovarian cancer who are scheduled to undergo primary surgical cytoreduction, interval debulking, or recurrent ovarian cancer surgery. For a full list of eligibility criteria, refer to Section 5.2 of the protocol.

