5 TREATMENT ASSIGNMENT

The study design results in an open-label single-arm for the assessment of efficacy and safety. There is (are) no comparator group(s), and it is anticipated that all participating patients will receive OTL38. However, some patients receiving OTL38 will be randomized to undergo lesion assessment under normal light only and will not undergo fluorescent imaging. The goal of the randomization is not the assignment of patients to a comparator group, but to guard against the

possible “under-calling” of lesions during the normal light assessment by creating the possibility that any patient, following evaluation by normal light, may not continue to assessment by fluorescent imaging. To achieve this safeguard, a blinded randomization of patients to undergo fluorescent imaging, or not, will occur after normal light assessment, but prior to fluorescent imaging or surgery. The randomization will be generated from a single centralized randomization.

[REDACTED]

Patients receiving OTL38 and randomized to not to undergo fluorescent imaging will be evaluated for safety only.

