8.1 Full Analysis Set (FAS)

The FAS for the primary analysis of the primary endpoint will include patients exposed to OTL38 and randomized to undergo fluorescent imaging (OTL38+Imaging) who:

- Were evaluated under both normal light and fluorescent light imaging, and
- Had central pathology and histology confirmation for at least one FR+ Ovarian Cancer lesion detected under normal light or fluorescent light imaging

For the evaluation of the primary efficacy endpoint, only the evaluable lesions contributed by FAS subjects will be considered (see Section 8.4). The FAS will also be referred to as the modified Intent-to-Treat (mITT) analysis set.

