13.3 Analytic Methods for Exploratory Endpoints

13.3.1 Sensitivities, False Positive Rates, and Positive Predictive Values

Sensitivities, FPRs, PPVs, and the inoperability rate for FR+ with ovarian cancer and other disease+/test+ configurations will be estimated following similar analytic approaches to that outlined above for the secondary efficacy endpoints. The FAS will be used for these analyses, but will be modified for the lesion type requirement as appropriate, without regard to the evaluable status of the lesions.

13.3.2 Proportion of Subjects With at Least One Additional Lesion Detected by OTL38 and Fluorescent Light Not Detected by Normal Light – Various Lesion Types

For other endpoints reflecting the proportion of patients with at least one additional lesion detected by OTL38 in combination with fluorescent light not detected by normal light, but for other cell types and FR outcomes, the point estimates and exact 95% CIs for the observed proportions will be provided. The statistical methods will be similar to those outlined above for the primary efficacy endpoint, except no formal hypothesis testing will be conducted and only the point estimates and CIs will be provided. The FAS will be used for these analyses, but will be modified for the lesion type requirement as appropriate. Unless otherwise specified, only evaluable lesions will be analyzed.

13.3.3 Number of Additional Lesions Detected by OTL38 and Fluorescent Light Not Detected by Normal Light – Various Lesion Types

Other endpoints estimating the mean number of additional evaluable fluorescent light positive lesions (of a specific type) not detected by normal light, will be estimated via a [REDACTED] model along with 95% CIs. [REDACTED]

[REDACTED] The point estimate for the average number of additional lesions will be provided along with the 95% CIs.

The analyses described above include patients with zero additional lesions detected by fluorescent light not detected by normal light. Analyses will also be conducted excluding patients with zero additional lesions detected by fluorescent light. F [REDACTED]

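### PPV for FR+ ovarian cancer is planned on the FAS, which requires a confirmed FR+ lesion; a raw pooled PPV on that set is at or above its value in all imaged patients

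*SAP*

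**What the plan says.** SAP 13.3.1 covers sensitivities, false positive rates, PPVs and the inoperability rate for FR+ ovarian cancer and for other disease/test combinations. On the analysis set it says: "The FAS will be used for these analyses, but will be modified for the lesion type requirement as appropriate". Protocol 8.2.5.4 agrees.

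To enter the FAS (SAP 8.1), a patient must be exposed to OTL38, randomized to imaging and evaluated under both lights, and must meet this condition: "Had central pathology and histology confirmation for at least one FR+ Ovarian Cancer lesion detected under normal light or fluorescent light imaging".

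The enrolled population is wider. SAP 4 describes patients "diagnosed with, or with a high clinical suspicion of, ovarian cancer". Protocol 5.2.2 excludes only "Known FR-negative ovarian cancer". Randomization to imaging, under SAP 5, "will occur after normal light assessment, but prior to fluorescent imaging or surgery". The design overview in SAP 3 states: "Efficacy will be assessed for patients undergoing both normal light and fluorescent light imaging". That sentence does not require confirmed cancer.

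For FPRp, SAP 13.2 says "The analysis will be conducted using the FAS". SAP 12.2 makes that endpoint a patient-level fraction, counting "folate positive ovarian cancer patients in whom all lesions, without regard to evaluable lesion status, detected by fluorescent light only are histologically negative".

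**The concern.** A PPV answers a question asked before pathology is available: if tissue fluoresces, how often is it FR+ ovarian cancer? The surgeon asks this of every patient imaged. Under SAP 13.3.1 the answer comes only from patients later shown to have at least one such lesion.

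Patients with benign disease, a non-ovarian cancer or an FR-negative ovarian cancer can be enrolled, imaged and then left out of this estimate. Protocol 3.2 itself puts FR expression at over 90% of epithelial ovarian cancers, not all. Their fluorescent lesions are all false positives for FR+ ovarian cancer. In the visible text, the only output clearly assured for those lesions is a line listing (SAP 14.7). A FAS-only PPV could therefore be read as applying to everyone imaged when it describes a narrower group. What is at stake is how a descriptive figure is interpreted and labelled.

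**Working it through.** **Plan's own figures.** The documents state no PPV, lesion count or expected number of patients outside the FAS. The one visible design figure is the minimum of 100 evaluable patients (Protocol synopsis). Its derivation is redacted and is not needed here; 100 serves only as an illustrative FAS size.

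**Direction.** Let TP and FP be the numbers of fluorescent lesions in FAS patients, with pathology read, that are and are not confirmed as FR+ ovarian cancer. Let F ≥ 0 be the number of fluorescent lesions with pathology read in imaged patients outside the FAS. A patient evaluated under both lights but outside the FAS has no confirmed FR+ ovarian cancer lesion, so she contributes no true positives.

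- PPV on the FAS = TP / (TP + FP)
- PPV in all imaged patients = TP / (TP + FP + F)

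The second cannot exceed the first. With TP > 0, they are equal only when F = 0. The same direction holds for a simple mean of patient-level PPVs, because the added patients contribute zeros. It need not hold for a conditional estimate from a mixed model.

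**Size, under assumed counts.** Take 100 FAS patients with 300 fluorescent lesions, and a FAS PPV of B. Let q be the share of imaged patients outside the FAS, so their number is m = 100q/(1 − q). Let h be the share of them with any fluorescent lesion with pathology read, and k the number of such lesions each. Then F = m × h × k, and PPV in all imaged patients = 300B / (300 + F).

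| Case (B = 75%, so 225 of 300 confirmed) | m | F | PPV, all imaged |
|---|---|---|---|
| No patients outside the FAS, or none with such lesions | – | 0 | 75.0% |
| q = 5%, h = 0.2, k = 1 | 5.3 | 1.05 | 74.7% |
| q = 10%, h = 0.4, k = 2 | 11.1 | 8.9 | 72.8% |
| q = 20%, h = 0.4, k = 3 | 25 | 30 | 68.2% |
| q = 20%, h = 0.6, k = 3 | 25 | 45 | 65.2% |

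The range from F = 1.05 to F = 45 is 59.8% to 52.2% if B = 60%, and 89.7% to 78.3% if B = 90%.

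Break-even from 75.0%: nine such lesions give 225/309 = 72.8%, a loss of about 2 points. Twenty-two give 225/322 = 69.9%, a loss of about 5 points.

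**FPRp, for contrast.** Suppose 10 of 100 FAS patients have only histologically negative fluorescence-only lesions, giving 10.0% (Wilson 95% interval 5.5% to 17.4%). Add 25 imaged patients from outside the FAS. If none of them is an event, the rate per imaged patient is 10/125 = 8.0%. If 10 are events, it is 20/125 = 16.0%. The direction is not fixed.

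**The case against.** The strongest objection is that no visible text plans a raw pooled PPV. SAP 13.3.1 refers back to the secondary-endpoint methods, most of which are redacted. The exploratory endpoint list is redacted too, and a generalized linear mixed model appears among the SAP's abbreviations. This stands: neither direction nor size can be claimed for the planned estimate, only for a raw pooled one. Redacted text, or the table shells kept in a separate document (SAP 1), may already hold an all-imaged figure.

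Second, the choice of the FAS is deliberate. SAP 13 assigns it to secondary and exploratory endpoints with modified criteria as appropriate, and the primary objective concerns patients with FR+ disease. This also stands, and the plan does not contradict itself. The clause allowing modification for lesion type may bring some non-FAS patients into other disease/test combinations. It does not help PPV for FR+ ovarian cancer, because the FAS already imposes that lesion type.

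Third, the effect may be small. In the laparoscopy-first group, laparotomy depends on cancer being detected (Protocol 5.2.1), which may reduce imaging of cancer-free patients. The 65.2% case also stacks three upper-end assumptions. Both points limit the size, but neither removes the possibility.

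A reader might infer that the FAS is also the wrong set for FPRp, or that it biases FPRp in a known direction. The documents support neither. FPRp is defined among folate positive ovarian cancer patients, so the FAS fits, and an all-imaged version would be a different estimand that could be higher or lower.

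**Conclusion.** The point holds for PPV for FR+ ovarian cancer. The FAS conditions on a result known only after surgery, imaged patients without that result can exist, and a raw pooled PPV on the FAS is then at or above its value in all imaged patients.

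This assumes that patients outside the FAS were evaluated under both lights and have no confirmed FR+ ovarian cancer lesion. A deviation, such as imaging without the normal-light evaluation, could break it.

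The size cannot be found from the documents. In the illustration starting from 75.0% it runs from zero to 9.8 points, with 2.2 points in the middle case, and every input except the 100 is assumed.

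A reader might infer that the trial's reported PPV will be inflated by a known amount. That goes too far, because the estimator and the PPV definition are not visible. The measure is exploratory and descriptive. The change is a cheap improvement to what the trial can report.

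**What to change.** Keep the FAS analysis and label its PPV as conditional on confirmed FR+ ovarian cancer. Add one supportive descriptive row giving the pooled PPV for FR+ ovarian cancer in all OTL38-exposed patients who underwent fluorescent imaging. Use the pathology available for excised lesions, and state how many imaged patients fall outside the FAS. None of this is needed if a redacted passage or the table shells already provide it.

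Optionally, give FPRp a second row among FAS patients with at least one fluorescence-only lesion. In the illustration above, if 30 of the 100 had such a lesion, the rate would be 10/30 = 33.3% (Wilson 19.2% to 51.2%). SAP 13.3.3 already reports lesion counts both with and without zero-lesion patients.

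The cost is one table row and a label, with no new test, alpha or sample size. SAP 14.7 already lists pathology and immunohistochemistry results with no stated limit to the FAS. Whether central reading covers every imaged patient cannot be confirmed, because the specimen-processing text is largely redacted. The downside for the sponsor is a possibly less favourable figure.

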13.3 Analytic Methods for Exploratory Endpoints

13.3.1 Sensitivities, False Positive Rates, and Positive Predictive Values

Sensitivities, FPRs, PPVs, and the inoperability rate for FR+ with ovarian cancer and other disease+/test+ configurations will be estimated following similar analytic approaches to that outlined above for the secondary efficacy endpoints. The FAS will be used for these analyses, but will be modified for the lesion type requirement as appropriate, without regard to the evaluable status of the lesions.

13.3.2 Proportion of Subjects With at Least One Additional Lesion Detected by OTL38 and Fluorescent Light Not Detected by Normal Light – Various Lesion Types

For other endpoints reflecting the proportion of patients with at least one additional lesion detected by OTL38 in combination with fluorescent light not detected by normal light, but for other cell types and FR outcomes, the point estimates and exact 95% CIs for the observed proportions will be provided. The statistical methods will be similar to those outlined above for the primary efficacy endpoint, except no formal hypothesis testing will be conducted and only the point estimates and CIs will be provided. The FAS will be used for these analyses, but will be modified for the lesion type requirement as appropriate. Unless otherwise specified, only evaluable lesions will be analyzed.

13.3.3 Number of Additional Lesions Detected by OTL38 and Fluorescent Light Not Detected by Normal Light – Various Lesion Types

Other endpoints estimating the mean number of additional evaluable fluorescent light positive lesions (of a specific type) not detected by normal light, will be estimated via a [REDACTED] model along with 95% CIs. [REDACTED]

[REDACTED] The point estimate for the average number of additional lesions will be provided along with the 95% CIs.

The analyses described above include patients with zero additional lesions detected by fluorescent light not detected by normal light. Analyses will also be conducted excluding patients with zero additional lesions detected by fluorescent light. F [REDACTED]

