1 PROTOCOL SYNOPSIS

Study Title	A Phase 3, Randomized, Single dose, Open-Label Study to Investigate the Safety and Efficacy of OTL38 Injection (OTL38) for Intra-operative Imaging of Folate Receptor Positive Ovarian Cancer
Sponsor	On Target Labs, Inc. [REDACTED]
Primary Objectives	
 To confirm the efficacy of OTL38 in combination with fluorescent light to detect additional Folate Receptor-positive (FR+) ovarian cancer lesions not detected by palpation and visualization under normal light in patients with FR+ ovarian cancer scheduled to undergo primary surgical cytoreduction, interval debulking, or recurrent ovarian cancer surgery
Secondary Objectives	
 To estimate the proportion of folate positive ovarian cancer patients in whom all lesions detected by fluorescent light only are histologically negative, the patient level False Positive Rate (FPRp) To estimate the Sensitivity and False Positive Rate for OTL38 in combination with fluorescent light with respect to the detection of FR+ ovarian cancer lesions confirmed by [REDACTED] pathology To assess the safety of using OTL38 and [REDACTED] Imaging System or Quest Spectrum Imaging System for intraoperative imaging [REDACTED]
Exploratory Objectives	
 To estimate the lesion inoperability rate for all lesions identified by fluorescent light only. To describe the diagnostic characteristics of OTL38 in combination with fluorescent light for lesions of various histological and pathological cell types To assess CA-125 levels before and after surgery To estimate the plasma pharmacokinetics (PK) of OTL38 in patients with FR+ ovarian cancer scheduled to undergo primary surgical cytoreduction, [REDACTED]
Study Design	
This is a phase 3, randomized, multi-center, single dose, open label, pivotal study in patients diagnosed with, or with high clinical suspicion of, ovarian cancer scheduled to undergo primary surgical cytoreduction, interval debulking, or recurrent ovarian cancer surgery.
 
[REDACTED]

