5.7.5 Pathology Samples

All excised lesions will be processed as outlined in [Section 5.7.1.2.1](#). Please refer to the site Manual for additional details.

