8.2.5 Efficacy Evaluations

8.2.5.1 Primary Analysis for the Primary Efficacy Endpoint

The primary analysis of the primary efficacy endpoint will be a one-sample test for a proportion via an exact binomial test using a two-tailed alpha level of 0.05.

[REDACTED]

8.2.5.2 *Sensitivity Analyses for the Primary Efficacy Endpoint*

Sensitivity analyses for the primary efficacy endpoint will be conducted separately for the Per-Protocol analysis sets. [REDACTED]

8.2.5.3 *Analytic Methods for Secondary Efficacy Endpoints*

The patient level False Positive Rate (FPR_p) will be analyzed descriptively, providing the point estimate and the two-sided 95% Wilson (score) confidence interval. [REDACTED]

8.2.5.4 *Analytic Methods for Other Endpoints*

Sensitivities, FPRs, PPVs and inoperability rates for FR+ with ovarian cancer and other disease+/test+ configurations will be estimated following similar analytic approaches to that outlined above for the secondary efficacy endpoints. The FAS will be used for these analyses, but will be modified for the lesion type requirement as appropriate, without regard to the evaluable status of the lesions.

For other endpoints reflecting the proportion of subjects with at least one additional lesion detected by OTL38 in combination with fluorescent light not detected by normal light, but for other cell types and FR outcomes, the point estimates and exact 95% CIs for the observed proportions will be provided. [REDACTED]

Other endpoints estimating the mean number of additional evaluable fluorescent light positive lesions (of a specific type) not detected by normal light, will be estimated [REDACTED]

[REDACTED]

The point estimate for the average number of additional lesions will be provided along with the 95% CIs.

[REDACTED]

[REDACTED]

Descriptive summary statistics for [REDACTED] pre-surgery (baseline), post-surgery, and the change from pre-surgery will be calculated along with the percent change. In addition, the number and percent of patients whose post-surgery [REDACTED] have increased, decreased, or remained the same as pre-surgery levels will also be provided. This analysis will use all patients with non-missing [REDACTED]

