13.4 Handling of Missing Data and Subject Withdrawals

For the primary efficacy endpoint, all patients included in the FAS with at least one evaluable lesion will be included in the primary analysis.

For secondary and exploratory efficacy endpoints, patient inclusion for the analysis of a specific endpoint will depend on the lesion type or patient subgroup under specific consideration.

In general, missing safety data will not be imputed with the possible exception of missing or partial dates for adverse events and concomitant medication.

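### The objective takes the inoperability rate over all fluorescent-only lesions, but the analysis plans it by pathology-defined lesion type, which biases it downward unless every inoperable lesion is sampled

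*SAP*

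**What the plan says.** The Exploratory Objectives in the protocol synopsis include: "To estimate the lesion inoperability rate for all lesions identified by fluorescent light only". This sets no pathology condition on the denominator.

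The analysis text words it differently. SAP 13.3.1 states: "Sensitivities, FPRs, PPVs, and the inoperability rate for FR+ with ovarian cancer and other disease+/test+ configurations will be estimated". The next sentence assigns these analyses to the FAS, which "will be modified for the lesion type requirement as appropriate, without regard to the evaluable status of the lesions". Protocol 8.2.5.4 has the parallel sentence in the plural: "Sensitivities, FPRs, PPVs and inoperability rates for FR+ with ovarian cancer and other disease+/test+ configurations will be estimated".

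Three other places bear on who and what is counted:

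- **FAS entry (SAP 8.1).** One condition is that the patient "Had central pathology and histology confirmation for at least one FR+ Ovarian Cancer lesion detected under normal light or fluorescent light imaging".
- **Pathology (Protocol 5.7.5).** The visible rule begins: "All excised lesions will be processed as outlined in". The section it points to, Protocol 5.7.1.2.1, is almost wholly redacted.
- **Missing data (SAP 13.4).** For secondary and exploratory endpoints, "patient inclusion for the analysis of a specific endpoint will depend on the lesion type or patient subgroup under specific consideration". The visible text gives no rule for a lesion without a tissue result.

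**The concern.** Sensitivity, false positive rate and positive predictive value cannot be computed without a tissue diagnosis. Inoperability can: it is the surgeon's finding about a lesion that lit up. Listing it with the other three makes entry to its denominator depend on pathology. Pathology is least likely to exist for the very lesions that the rate is meant to count.

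The rate tells a reader how often fluorescence shows a lesion that the surgeon cannot remove. An estimate that loses some of those lesions from numerator and denominator together makes the product look better on that question. It also no longer answers the question set in the objective.

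The FAS adds a second, probably smaller, selection. An imaged patient with no confirmed FR+ ovarian cancer lesion is left out. Her fluorescent-only lesions, removable or not, are then absent from a rate whose objective covers all such lesions.

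**Working it through.** The visible text gives no inoperability figure, so there is nothing to reproduce. The check compares the passages and then illustrates direction and size.

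**Comparing the denominators**

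1. Synopsis objective: all fluorescent-only lesions, with no tissue result needed.
2. SAP 13.3.1 and Protocol 8.2.5.4: lesions in a disease+/test+ configuration. A fluorescent-only lesion is test+ by definition, so the condition that does the selecting is disease+. FR+ ovarian cancer status rests on pathology and histology (SAP 8.1).
3. A fluorescent-only lesion with no tissue result belongs to the denominator in 1 but cannot be assigned to a configuration in 2.

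**Inputs for the illustration (all assumed, none given in the visible text)**

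- r, the true share of fluorescent-only lesions that are inoperable: 0.05 to 0.30.
- b, the share of inoperable lesions that still have a tissue diagnosis: 0 to 1.
- All operable lesions have pathology.
- r and b are the same for each lesion type.

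**Formula**

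Planned rate = r·b / (r·b + 1 − r)

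**Worked case, r = 0.10**

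- b = 0: 0 / 0.900 = 0%
- b = 0.25: 0.025 / 0.925 = 2.7%
- b = 0.5: 0.050 / 0.950 = 5.3%
- b = 0.75: 0.075 / 0.975 = 7.7%
- b = 1: 0.100 / 1.000 = 10%

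**Full range**

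| True rate r | b = 0 | b = 0.25 | b = 0.5 | b = 0.75 | b = 1 |
|---|---|---|---|---|---|
| 5% | 0% | 1.3% | 2.6% | 3.8% | 5% |
| 10% | 0% | 2.7% | 5.3% | 7.7% | 10% |
| 20% | 0% | 5.9% | 11.1% | 15.8% | 20% |
| 30% | 0% | 9.7% | 17.6% | 24.3% | 30% |

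**Relaxing one assumption**

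If only 90% of operable lesions have pathology, the formula becomes r·b / (r·b + 0.9·(1 − r)). At r = 0.10 it gives 0%, 3.0%, 5.8%, 8.5% and 11.0% for the same five values of b. The general condition is that the planned rate is too low whenever inoperable lesions are sampled less often than operable ones.

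**With the objective's denominator**

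The rate is r itself, whatever b is, because no tissue result is needed.

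**The case against.** The strongest reply is that the decisive text is hidden. The exploratory endpoints (Protocol 6.3, SAP 12.3), the intra-operative procedures (Protocol 5.7.1.2.1), the lesion-level secondary methods (SAP 13.2) and the surgical reporting forms are redacted. They may define inoperability, call for tissue from such lesions, or specify an overall rate with the objective's denominator. This stands. It means that the size of the bias cannot be stated and that no definition can be called missing.

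A second reply is grammatical. The SAP has a singular rate at the end of a list, so the configuration phrase might belong only to the three diagnostic measures. SAP 8.4 attaches similar wording to those three without inoperability, although redacted text precedes it there. The plural in Protocol 8.2.5.4 points the other way, to one rate per configuration. If an overall rate does exist in the redacted text, the rates by type would still carry the bias.

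Third, the FAS effect may be slight. Entry needs only one confirmed lesion under either light, and patients known before surgery to have inoperable miliary disease are excluded. This is fair. It is why the FAS version should be kept alongside and not dropped.

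A reader might go further and infer that an inoperable lesion never has pathology, so that the planned rate is near zero by construction. The documents do not support that. Protocol 5.7.5 says how excised lesions are handled; it does not say that other lesions go unsampled. In the illustration the rate is exactly zero only at b = 0, and at b = 0.5 a true 10% still shows as 5.3%.

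**Conclusion.** The point holds as a conflict between the stated objective and the visible analysis sentences in both documents, with a predictable direction of bias. Rates by pathology-defined type are too low when inoperable lesions are sampled less often than operable ones. If all operable lesions have pathology, the bias disappears only when every inoperable lesion is sampled.

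The size is unknown. Under the stated assumptions a true 10% would be reported as anything from 0% to 10%, depending wholly on b. That inoperable lesions are less often sampled is a reasonable inference from what inoperable means, but the visible text does not state it.

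The consequence is limited to one exploratory estimate. The primary test and its analysis set are untouched.

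**What to change.** In SAP 13.3.1 and Protocol 8.2.5.4:

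1. Take the inoperability rate out of the disease+/test+ list and give it its own sentence.
2. Make the main estimate the number of fluorescent-only lesions recorded as inoperable, divided by all fluorescent-only lesions whatever their pathology, among patients who underwent fluorescent imaging. Report the FAS version alongside.
3. Keep rates by lesion type as supplementary only.
4. Show how many inoperable lesions had a tissue diagnosis and how many did not, so that a reader can judge the rates by type.

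If a redacted section already defines the rate this way, the change only aligns the visible sentences with it.

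The cost is wording, a little more tabulation and a possibly less favourable rate. The objective already requires operability to be known for each fluorescent-only lesion, and nothing here changes surgical or sampling practice.
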